9.2.7 Registry Visits

9.2.7.1 Enrolment Visit

Investigators at participating sites will identify patients who fulfil the inclusion and exclusion criteria. Written informed consent should be obtained prior to enrolment according to local regulations, and when inclusion and exclusion criteria have been checked.

All reported measures will be performed by the paediatric endocrinologist.

The following participant history and clinical data will be recorded.

- Demographics:
 - Sex
 - Date of birth (month and year)
 - Birth weight and length
 - Gestational age
 - Previous and current height, sitting height and weight measurements
- Parental heights (biological relatives only)
- Medical history including:
 - Anorexia nervosa, asthma, attention deficit disorder, carpal tunnel syndrome, cystic fibrosis, diabetes, oedema, enlarged tonsils or adenoids, headache, hearing loss, hypoglycaemia (documented or suspected - documented means blood level glucose < 50 mg/dL or 2.78 mmol/L), hypothyroidism, neoplasia, organomegaly, otitis media, retinopathy, scoliosis, seizures, sleep apnoea, slipped capital femoral epiphysis, snoring, tonsillectomy and/or adenoidectomy, cardiomegaly and any other significant medical history
- Personal and family history of neoplasia
- Chronic concomitant medications including:
 - Antibiotics, medication for attention deficit disorder, anti-depression medication, aromatase inhibitors, gonadotrophin releasing hormone agonists, thyroid

hormone, GH, androgens, oestrogens, glucocorticoids, bronchodilators, other psychiatric medications and other chronic medications

- Most recent IGF-1 concentrations including:
 - Unit of measure, level and IGF-1 SD score, date acquired, name of assay, normal ranges
- IGF-1 generation test (if locally applicable) including test date, dose of GH used, total number of doses, baseline IGF-1, stimulated IGF-1 and IGF-1 laboratory kit
- GH concentrations including:
 - Basal/random GH
 - Highest stimulated GH
- Serum insulin-like growth factor-binding protein 3 (IGFBP3; serum level in ng/ml and name of assay)
- GH-binding protein (GHBP; level in pmol/L and name of assay)
- Genetic tests performed (Yes/No) and date and results of any tests performed including:
 - GH gene deletion/mutation, IGF-1 gene deletion/mutation, fibroblast growth factor (FGF) deletion/mutation, gene encoding non-receptor type of protein tyrosine phosphatase SHP-2 (PTPN11) deletion/mutation, GHR gene deletion/mutation, deletion of exon 3 of the GHR (D3-GHR), signal transducer and activator of transcription 5b (STAT5b) deletion/mutation, acid-labile subunit (ALS) deletion/mutation, short stature homeobox-containing gene (SHOX) deletion/mutation, pappalysin 2 (PAPPA2) gene deletion/mutation, karyotype, any other genetic tests performed (e.g. whole exon sequencing)
- Bone age and method (e.g. Greulich and Pyle (GP) method) and date of X-ray, echocardiogram and funduscopy
- Most recent physical examination including:
 - Pubertal (Tanner) stage: pubic hair, testicular volume, breast development
 - Dysmorphic features
- Pregnancy test for female patients of childbearing potential. Any pregnant patients should be excluded from the registry.
- Predicted adult height (PAH)
- Date of growth failure (short stature) diagnosis
- Diagnosis of SPIGFD (according to the local approved definition of SPIGFD) and date of diagnosis with corresponding levels of IGF-1 and GH, and IGF-1 SDS and height SDS
- Associated aetiologies, all that apply should be ticked in the list below: GH gene deletion with anti-GH antibodies, small for gestational age, idiopathic short stature, Noonan syndrome, Prader-Willi syndrome, chondrodysplasia, bone dysplasia, insulin resistance syndrome (e.g. leprechaunism, Rabson-Mendenhall syndrome), diabetes mellitus, Russell Silver, or other
- Previous therapy:
 - GH: duration (months), maximum dose (mg/kg/day), start of maximum dose date and height, end of maximum dose date and height
 - Steroids type (specify, e.g. GH, IGF-1, steroid hormones such as sex steroids (testosterone and oestradiol))

- IGF-1, name of preparation (rhIGF-1, rhIGF-1/IGF-1/IGFBP3, other), in a clinical trial (Yes/No) or compassionate use (Yes/No)
- Increlex® therapy
 - Starting Increlex® dose (mg/kg or mcg/kg)
 - Starting Increlex® dose date
 - Planned posology of Increlex® injections (per day) at start date
 - Dose escalation planned (Yes/No)
- QoL assessment using EQ-5D version EQ-5D-Y on participants aged 4 and over (see Section 9.3.2.5).

9.2.7.2 *Follow-up Visits (in Treatment Period)*

The following data will be recorded:

- Visit date
- Chronic concomitant medications including:
 - Antibiotics, medication for attention deficit disorder, anti-depression medication, aromatase inhibitors, gonadotrophin releasing hormone agonists, thyroid hormone, GH, androgens, oestrogens, glucocorticoids, bronchodilators, other psychiatric medications and other chronic medications
- IGF-1 concentrations (unit of measure, level, date acquired, name of assay) including both absolute value and SD or percentile of assay-specific reference, if references available
- Serum IGFBP3 (serum level in ng/ml and name of assay)
- Bone age and method (e.g. GP method) and date of X-ray, echocardiogram and funduscopy
- Physical examination including:
 - Current height, sitting height and weight measurements and FAH (if available)
 - Pubertal (Tanner) stage: pubic hair, testicular volume, breast development
- Increlex® therapy: all doses changes (including interruptions) with posology, dates and reasons for change will be collected. For drug compliance, number of missing doses will also be collected
- All AEs, including SAEs, AESI and targeted AEs (see Section 11.1.5), and special situations. Onset and recurrence of benign and malignant neoplasias will be considered as AESI and should also be reported as SAE
 - For hypoglycaemia (documented or suspected), time from last Increlex® dose to time of event, blood glucose level (if available) and event resolution without intervention other than feeding (Yes/No) should also be collected
- Discontinuation of therapy
 - Date of last dose
 - Reason for discontinuing therapy, the most appropriate response should be selected: attained adult height, AE, lost to follow-up, noncompliance, participant/parent/legally authorised representative decision, financial/insurance, changed physician, lack of effectiveness, shortage of Increlex®, physician decision, COVID-19 or other (if other the reason should be specified)

- QoL assessment using EQ-5D version EQ-5D-Y on participants aged 4 and over at year one, at end of treatment and at FAH (see Section 9.3.2.5).

9.2.7.3 *Post-treatment Visits*

The importance of the follow-up visits, including at least visits at years 2 and 5 after the end of treatment, should be noted. The following data will be recorded:

- Visit date
- Concomitant medications including:
 - Antibiotics, medication for attention deficit disorder, anti-depression medication, aromatase inhibitors, gonadotrophin releasing hormone agonists, thyroid hormone, GH, androgens, oestrogens, glucocorticoids, bronchodilators, medication for diabetes, medication for high blood pressure, medication for malignancy, medication for hyperlipidaemia, medication for immune system disorders, medication for coagulation disorders, other psychiatric medications and other chronic medications
- IGF-1 concentrations (unit of measure, level, date acquired, name of assay)
- Bone age and method (e.g. GP method) and date of X-ray (in case adult height not reached), echocardiogram and funduscopy
- Physical examination including:
 - Current height, sitting height and weight measurements and FAH (if available)
 - Pubertal (Tanner) stage: pubic hair, testicular volume, breast development
- All AEs, including SAEs, AESI and targeted AEs (see Section 11.1.5), and special situations. Onset and recurrence of benign and malignant neoplasias will be considered as AESI and should also be reported as SAE
 - For hypoglycaemia (documented or suspected), time from last Increlex® dose to time of event, blood glucose level (if available) and event resolution without intervention other than feeding (Yes/No) should also be collected
- QoL assessment using EQ-5D version EQ-5D-Y at FAH (see Section 9.3.2.5).

9.2.8 *Registry Discontinuation/Withdrawal*

The participant will be withdrawn from the registry:

- If informed consent is withdrawn (participant/parent or legally authorised representative decision; the participant must be informed that they may decide to withdraw from the registry at any time without any effect on their treatment and the normal follow-up of the disease);
- At the end of the post-treatment follow-up (5 years after stopping treatment or at adult height if later);
- If the participant is lost to follow-up;
- If the participant is included in a clinical trial for growth retardation.

If a participant is withdrawn from the registry, the date and primary reason for withdrawal should be recorded in the eCRF as well as if the participant stopped Increlex® therapy or not.

Investigators may decide to stop their participation in the registry at any time without consequences on the normal participant follow-up. If this occurs, every effort should be made to transfer care of the participant to a new physician to enable the participant to continue in the registry.

9.2.9 *Treatment Discontinuation*

If benign or malignant neoplasia develops, Increlex® treatment should be discontinued definitely and appropriate expert medical care sought. If a US patient develops benign neoplasm, Increlex® treatment can continue.

Increlex® treatment may be discontinued in the event of any SAEs, AEs or special situations deemed by the Investigator to warrant treatment discontinuation.

Discontinuation of treatment due to AEs should be distinguished from discontinuation/withdrawal from the registry due to participant/parent decision or end of post-treatment follow up. In all cases due to AEs, the Investigator must ensure that the participant receives appropriate medical follow up and this should be properly documented in the participant's medical records.

All participants discontinuing Increlex® treatment will be followed up in the registry in the post-treatment period (unless consent is withdrawn).

9.3 *Endpoints and Variables*

9.3.1 *Endpoints*

9.3.1.1 *Primary Endpoints*

- Incidence of SAEs (including AESI of neoplasia), targeted AEs, all AEs, deaths and withdrawals due to AEs during Increlex® treatment.

9.3.1.2 *Secondary Endpoints*

- Incidence of SAEs (including AESI of neoplasia), targeted AEs, all AEs, deaths, withdrawals due to AEs, special situations and concomitant medications within the 5-year post-treatment period, overall and in the subset of children and adolescents exposed to Increlex® for at least 3 cumulative years excluding interruptions;
- Incidence of special situations and concomitant medications during Increlex® treatment;
- Changes from baseline for the following effectiveness variables: height SDS, height velocity, body mass index (BMI) SDS, bone age development, pubertal (Tanner) stage;
- Estimation of differences between PAH and FAH;
- Modelisation to identify predictive factors of height SDS change, height velocity, FAH, pubertal (Tanner) stage, bone age development;
- Description of Increlex® therapy exposure (dose and duration) and compliance;
- Description of effectiveness parameters (height SDS, height velocity) according to average dose received and according to dose ranges (e.g. 4 dose ranges (≤ 50 , $]50-80]$, $]80-110]$, $> 110 \mu\text{g/kg BID}$). This analysis will support the description of the lowest effective dose;
- Biological assessments (IGF-1 levels, GH concentrations, serum IGFBP3);
- Genetic test results;
- Description and evolution of QoL in participants aged 4 and over using EQ-5D version EQ-5D-Y including changes from baseline at year one, at end of treatment and at FAH;
- Description of neoplasia (benign and malignant) and hypoglycaemia according to the timeframe of occurrence (e.g. within the first 3 years after start of treatment, between 3 and 5 years and over 5 years).

9.3.2 *Variables*

9.3.2.1 *Demographic and Baseline Variables*

The registry will collect the following data:

- Demographic data on children and adolescents receiving Increlex® treatment: sex, date of birth (month and year), birth weight and length, gestational age, previous and current height, sitting height and weight;
- Parental heights (biological relatives only);
- Baseline height, sitting height, weight, bone age and method, echocardiogram, funduscopy and pubertal (Tanner) stage;
- Pregnancy status;
- PAH;
- Diagnosis of SPIGFD (documented by height SDS; IGF-1 levels and IGF-1 SDS; GH levels), date of diagnosis and associated aetiologies, and date of growth failure (short stature) diagnosis, if different from SPIGFD diagnosis date;
- IGF-1 generation test results and IGF-1/IGFBP3 concentrations;
- GH concentrations including basal/random and highest stimulated;
- Serum IGFBP3;
- GHBP;
- Genetic test results and date of genetic testing;
- Current and previous illnesses including congenital conditions and neoplasia;
- Previous and concomitant medications;
- Personal and family history of neoplasia;
- Prior growth-promoting therapies: GH, IGF-1, steroid hormones such as sex steroids (testosterone and oestradiol);
- Baseline QoL assessment using EQ-5D version EQ-5D-Y.

9.3.2.2 *Safety Variables (Primary Analyses; Treatment Period and Secondary Analyses; Treatment and Post-treatment Follow-up Periods)*

Data on the following safety variables will be collected from enrolment to the end of the post-treatment follow-up period:

- For all AEs, irrespective of causality, including SAEs, AESI and targeted AEs, start/end date, time to onset, nature, severity, seriousness, causality assessment, any treatment administered for the AE, action taken and outcome;
- Deaths, irrespective of causality, including date and cause of death;
- Special situations, irrespective of causality, including start/end date, category, description, whether the special situation led to an AE and outcome;
- Concomitant medications including concomitant treatment with GH, with start/end dates;
- Echocardiography and funduscopy results.

9.3.2.3 *Effectiveness Variables (Secondary Analyses; Treatment and Post-treatment Follow-up Periods)*

Data on the following effectiveness variables will be collected at enrolment, during treatment and after the end of treatment:

- Height and sitting height;
- Weight;
- Pubertal (Tanner) stage: pubic hair, testicular volume, breast development;
- Bone age;
- IGF-1 concentrations;
- IGFBP3 (treatment period only);
- FAH.

9.3.2.4 *Treatment Variables (Secondary Analyses; Treatment Period)*

Data on the following treatment variables will be collected from start to end of treatment:

- Dose of Increlex® at the start of treatment (mg/kg or mcg/kg), mode of administration and date of first Increlex® intake;
- Any dose adjustments and dose interruptions (including adjusted dose and dates) throughout the study including reasons for adjustment;
- Dose of Increlex® at the end of treatment (mg/kg or mcg/kg) and date of last Increlex® intake;
- Reason for discontinuing therapy (most appropriate response): attained adult height, AE, lost to follow-up, noncompliance, participant/parent/legally authorised representative decision, financial/insurance, changed physician, lack of effectiveness, shortage of Increlex®, COVID-19 or other.

9.3.2.5 *Quality of Life Variables (Secondary Analyses; Treatment and Post-treatment Follow-up Periods)*

Data for the following QoL assessments will be collected at baseline (start of treatment), at year one, at end of treatment and at FAH:

- Changes in QoL assessment using EQ-5D version EQ-5D-Y.

The QoL of participants will be assessed using the EQ-5D-Y paediatric questionnaire, a child-friendly standardised measure of health status developed by the EuroQol Group, denoted 'Youth' as being adequate for both children and adolescents [24].

The EQ-5D-Y consists of two pages, a descriptive system and a visual analogue scale (VAS). The descriptive system comprises five dimensions, using child-friendly wording: mobility; looking after myself; doing usual activities; having pain or discomfort; feeling worried, sad or unhappy. Each dimension has three levels: no problems/no pain/not worried, some problems/some pain/a bit worried, a lot of problems/a lot of pain/very worried, from which the respondent chooses the most appropriate. The EQ VAS records the respondent's self-rated health on a 0-100 vertical VAS from 'The best health you can imagine' to 'The worst health you can imagine'.

Participants aged 8+ who are able to fill in the EQ-5D-Y themselves will self-complete the questionnaire and VAS. The EQ-5D-Y proxy version, designed for a proxy (parent or legally authorised representative) to rate how he/she rates the health of the child, is recommended for younger children and can be applied to children aged from 4-7 years and to children of 8+ who

are not able to fill in the EQ-5D-Y themselves. As the minimum age recommended for the proxy version is 4 years, participants between 2 and 4 years of age will not be included in the QoL assessments.

The version used for each participant should be clearly documented and a copy of the questionnaire retained in their medical records.

A country-specific local language version will be used for each country.

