8.2.2 Secondary Objectives

- To describe long-term safety data, for at least 5 years after the end of Increlex® therapy, in children and adolescents who have received Increlex® therapy, regardless of treatment duration and adult height;
- To describe long-term safety data at 2 and 5 years after the end of Increlex® therapy, for a subset of children and adolescents who have been exposed to Increlex® therapy for at least 3 cumulative years excluding interruptions, regardless of adult height;
- To describe Increlex® effectiveness throughout the study until the participant reaches adult height;
- To identify predictive factors of the main effectiveness parameters by modelisation of height velocity, FAH, height SDS change, timing and progression of puberty, bone age development;
- To evaluate Increlex® therapy exposure (dose and treatment duration) and compliance;
- To determine the lowest effective dose of Increlex® defined as the cut-off dose under which there is no further effect on the height velocity anymore (short-term evaluation: 1-year height velocity);
- To assess QoL during Increlex® therapy and in the post-treatment period (using EQ-5D version EQ-5D-Y (paediatric questionnaire));
- To describe the timeframe of the occurrence of neoplasia (benign and malignant) and hypoglycaemia.

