- b A negative pregnancy test must be obtained and documented for all female patients of childbearing potential prior to enrolment/treatment with Increlex®. It is also recommended that all female participants of childbearing potential use adequate contraception during treatment
- c Biological relatives only
- d List of targeted AEs during the post-treatment period is adjusted (see Section 11.1.5)
- e Including dysmorphic features
- f GH, IGF-1 and IGFBP3 levels will be performed by local laboratory (assay has to be documented)
- g Prior to treatment with Increlex®
- h In case of adult height not reached
- i QoL assessments at baseline (start of treatment), at year one, at end of treatment and at Final Adult Height

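### Post-treatment quality of life is scheduled only at final adult height, which can fall on treatment, so participants rated at or before their last dose give no scheduled post-treatment value

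*Protocol*

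**What the plan says.** The objective in Protocol Section 8.2.2 is "To assess QoL during Increlex® therapy and in the post-treatment period", and the heading of Section 9.3.2.5 likewise names both periods.

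The timing statements agree with one another:

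- Section 9.3.2.5: "Data for the following QoL assessments will be collected at baseline (start of treatment), at year one, at end of treatment and at FAH".
- Table 1, footnote i, which applies to the enrolment, treatment and post-treatment columns: "QoL assessments at baseline (start of treatment), at year one, at end of treatment and at Final Adult Height".
- Section 9.2.7.2, treatment-period visits: "QoL assessment using EQ-5D version EQ-5D-Y on participants aged 4 and over at year one, at end of treatment and at FAH".
- Section 9.2.7.3, post-treatment visits: "QoL assessment using EQ-5D version EQ-5D-Y at FAH (see Section 9.3.2.5".

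The endpoint in Section 9.3.1.2 is a description of QoL "including changes from baseline at year one, at end of treatment and at FAH". Section 9.7.2.6 describes the five EQ-5D-Y dimensions and the visual analogue scale at each timepoint, with change from baseline. It says nothing about whether the participant was on or off treatment at FAH.

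Both visit lists carry the item "Current height, sitting height and weight measurements and FAH (if available"), so FAH may be recorded in either period. Section 9.2.7.2 lists the reasons for stopping: "the most appropriate response should be selected: attained adult height, AE, lost to follow-up, noncompliance" and others. Section 9.2.4.3 sets post-treatment follow-up at 5 years or more for every participant, and Section 9.2.7.3 stresses visits at least at years 2 and 5.

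**The concern.** The objective is framed by treatment period, but the one post-treatment rating is tied to a growth milestone. That milestone has no fixed position relative to the last dose. It may come during treatment, at the stopping visit, or some years later in a child who stopped early.

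Two things are at stake. First, post-treatment QoL is scheduled for some participants and not for others, and what separates the two groups is whether treatment continued up to adult height. Those who did not continue are a selected group. Second, a change from baseline at FAH has no single meaning. It can combine ratings made under treatment, ratings that are also the end-of-treatment rating, and ratings made well after stopping. A reader could not take it as describing QoL in either period.

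**Working it through.** The protocol gives no figure to reproduce. The check follows each pathway through the schedule and then expresses the consequence algebraically.

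**Scheduled ratings by pathway** (Sections 9.2.7.1 to 9.2.7.3; Table 1, footnote i)

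| Pathway | On treatment or at its end | After treatment |
|---|---|---|
| FAH rated while still treated | baseline, year one, FAH, end of treatment | none |
| FAH rated at the stopping visit | baseline, year one, one rating serving as both end of treatment and FAH | none |
| FAH rated after the last dose | baseline, year one, end of treatment | one, at FAH, at an unfixed time since stopping |

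In the first two rows at least 5 years of follow-up pass with no scheduled QoL, although visits are requested at years 2 and 5. No other section adds a QoL timepoint.

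**Size.** Let

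- a = share of participants whose FAH is rated at or before the last dose;
- f = share of the remainder (those who stop before FAH is rated) who go on to have a recorded FAH rating.

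The protocol gives neither. Assuming that everyone in the first group has an FAH rating:

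- share with a post-treatment value = (1 − a)f, which is at most 1 − a;
- share of FAH ratings that are not post-treatment = a / (a + (1 − a)f).

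With assumed values:

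| a | Upper limit, 1 − a | (1 − a)f at f = 0.6 | Not post-treatment, f = 1 | Not post-treatment, f = 0.6 |
|---|---|---|---|---|
| 0.3 | 70% | 0.7 × 0.6 = 42% | 30% | 0.3/0.72 = 41.7% |
| 0.5 | 50% | 0.5 × 0.6 = 30% | 50% | 0.5/0.80 = 62.5% |
| 0.7 | 30% | 0.3 × 0.6 = 18% | 70% | 0.7/0.88 = 79.5% |

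The second share equals a only if every early stopper is followed to a recorded FAH. Losses among early stoppers raise it.

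**The case against.** The strongest reply has five parts.

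- **The objective does not promise more.** It does not say every participant, or fixed times since stopping. Early stoppers are followed until FAH, beyond 5 years if necessary, so an off-treatment rating is scheduled for them. Anchoring QoL on the growth outcome is a defensible choice in a descriptive safety registry. This stands as far as it goes, but it still leaves the post-treatment half of the objective mainly to early stoppers.
- **The split belongs in the analysis plan.** A reader might infer that the protocol requires on- and off-treatment FAH ratings to be pooled. It does not; it is silent. Visit dates and the date of last dose are collected, so an analysis plan could separate them. This stands for the table. It does not answer the collection gap, because an analysis plan cannot create ratings that were never scheduled.
- **FAH is not operationally defined.** A reader might infer that every child who stops on attaining adult height gives no post-treatment value. The protocol does not support that: FAH may be confirmed at a visit after the last dose, which would yield an early off-treatment rating. The point therefore holds only for those rated at or before the last dose.
- **Early stopping is not always related to outcome.** Besides adverse events, noncompliance and lack of effectiveness, the list includes product shortage, finance or insurance, change of physician and COVID-19. It would be wrong to describe early stoppers as treatment failures. They are still selected, in that treatment did not run to adult height.
- **The instrument is for youth.** Section 9.3.2.5 describes the EQ-5D-Y as suited to children and adolescents. Someone stopping at 16 to 18 would be 21 to 23 at the year 5 visit. This stands, and the remedy must deal with it.

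**Conclusion.** The point holds in this limited form. Followed as written, the schedule gives no post-treatment QoL for participants whose FAH is rated at or before the last dose. It leaves the post-treatment part of the objective mainly to those who stopped before adult height. It also allows the FAH summary to mix ratings from both periods.

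The size is unknown. The protocol reports neither the share rated at or before the last dose nor follow-up to FAH among early stoppers. The percentages above illustrate assumed values and are not estimates for this registry. Nor does the protocol say how common any pathway is; treatment continuing beyond FAH may be rare, since closed epiphyses are listed among the contraindications.

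The matter concerns one secondary, descriptive objective and does not touch the primary safety analysis. It is still worth correcting: one part costs almost nothing, and the registry is open-ended, so a change would benefit current and future participants.

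**What to change.** 1. **Analysis (Section 9.7.2.6).** Report QoL at FAH separately for FAH rated up to the last dose and FAH rated after it, giving time since last dose for the latter. Call only the latter post-treatment. Do not count a rating that is also the end-of-treatment rating as post-treatment. This uses dates already collected and costs only programming.

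2. **Collection (Section 9.2.7.3 and Table 1, footnote i).** Add QoL at the year 2 and year 5 post-treatment visits, which the protocol already requests, and state which EQ-5D version applies to participants who are adults by then. If a different version is used, say how its results will be set beside the EQ-5D-Y baseline.

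3. **Alternative to step 2.** Narrow the objective in Section 8.2.2 to what is collected: QoL during treatment, at its end and at FAH.

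The cost of step 2 is a short questionnaire (two pages for the EQ-5D-Y) at visits already requested; Section 9.4 already allows QoL as an exception to routine-care data. It also needs a protocol amendment. If that is classed as substantial, Section 9.11 calls for EMA assessment and approval, and Section 9.13 for new written consent from enrolled participants. Bundling it with another planned amendment would limit that burden.

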Effectiveness analyses will be based on the Registry Population.

The raw values of the following effectiveness parameters will be described at different timepoints (every 6 months from the start of treatment) as well as the change from baseline: height SDS, height velocity, BMI SDS, bone age development, pubertal stage.

For participants who reached the FAH, the estimation of the difference between the PAH and the FAH will be presented.

Main effectiveness parameters (height SDS, height velocity) will be described according to average dose received over the course of the study and according to dose ranges (e.g. 4 dose ranges (≤ 50 , $]50-80]$, $]80-110]$, $> 110 \mu\text{g/kg BID}$)). This analysis will support the description of the lowest effective dose.

Multivariate linear regression analyses will be used to identify predictive factors of height SDS change, height velocity, bone age development after 1 year of treatment or more. The same method will be used to assess the predictive factors of FAH.

The Cox regression model including covariates as sex, age or height SDS at start of Increlex® will be used to estimate the time from start of treatment to reach the puberty for a subset of prepubertal patients at start of Increlex®.

Biological assessments (IGF-1, IGFBP3), raw values and change from baseline, will be described at different timepoints.

Exposure to Increlex® Therapy

The treatment duration as well as the dose of Increlex® at each timepoint (initiation, 3 months, 6 months, 1 year, and every 6 months thereafter) will be described.

Duration of post-treatment follow-up will also be summarised.

Quality of Life Analysis

The QoL of participants aged 4 and over will be assessed using the EQ-5D-Y paediatric questionnaire (see Section 9.3.2.5 for details).

The 5 dimensions/domains (mobility; looking after myself; doing usual activities; having pain or discomfort; feeling worried, sad or unhappy) will be described at each timepoint as well as the evolution from baseline. The VAS will be described as a quantitative parameter at each timepoint as well as the change from baseline.

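### EQ-5D-Y change from baseline is described without regard to version, so for children who move from proxy to self-report it mixes a change of rater with change in health

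*Protocol*

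**What the plan says.** Section 9.3.2.5 ties the rater to age. For older children, "Participants aged 8+ who are able to fill in the EQ-5D-Y themselves will self-complete the questionnaire and VAS". The proxy version "is recommended for younger children and can be applied to children aged from 4-7 years and to children of 8+ who" cannot complete it themselves. Below the proxy version's minimum age there is no assessment: "participants between 2 and 4 years of age will not be included in the QoL assessments". Section 9.2.1 admits participants from 2 to 18 years, so starts at 4 to 7 are eligible.

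The timing is in the same section: "Data for the following QoL assessments will be collected at baseline (start of treatment), at year one, at end of treatment and at FAH". The endpoint in section 9.3.1.2 covers all of these children together: "Description and evolution of QoL in participants aged 4 and over using EQ-5D version EQ-5D-Y including changes from baseline at year one", and the sentence goes on to end of treatment and FAH.

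Section 9.7.2.6 gives the analysis. The five dimensions "will be described at each timepoint as well as the evolution from baseline". For the scale, "The VAS will be described as a quantitative parameter at each timepoint as well as the change from baseline". Neither sentence mentions version. Section 9.3.2.5 does require that "The version used for each participant should be clearly documented", with a copy of the questionnaire kept in the medical records. Version is not among the example subgroups in section 9.7.3, and the limitations in section 9.9 do not mention it.

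**The concern.** The proxy form records a parent's view of the child's health. The self-completed form records the child's own view. Subtracting one from the other is not a change in a single measure: any systematic difference between the two raters enters the result even if health is unchanged.

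The switch follows age, so for able children it goes from proxy to self and becomes more common with time since the start of treatment. There is no comparator group in which the same switch would occur and cancel. At stake is the interpretation of one secondary objective, quality of life during and after therapy. The later timepoints are the most exposed.

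**Working it through.** The protocol states no figure on this point, so there is none to reproduce. The check has two parts.

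**Who switches, from the age rule**

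- Start below 4: no baseline assessment, so no change from baseline.
- Start at 4 to 6: proxy at baseline and still proxy at year one. Self-report at end of treatment only if treatment continues past age 8 and the child is able.
- Start at 7: proxy at baseline, self-report by year one if able.
- Start at 4 to 7, assessed at FAH: nearly all who are able have switched, because FAH falls after age 8.
- Start at 8 or over and self-completing throughout: never affected.
- Unable to self-complete at 8 or over: proxy throughout.

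**How large the effect could be**

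Assumptions, none of them in the documents: start ages spread evenly over 4 to under 18 (14 years), every child able to self-complete from 8, and both assessments available for every child. The proxy-baseline band, 4 to under 8, is 4 years wide.

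Share of proxy-baseline children who have switched after t years = min(t, 4)/4. Share of all pairs = min(t, 4)/14.

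| Years since start | Of proxy-baseline children | Of all pairs |
|---|---|---|
| 1 | 1/4 = 25% | 1/14 = 7.1% |
| 2 | 2/4 = 50% | 2/14 = 14.3% |
| 3 | 3/4 = 75% | 3/14 = 21.4% |
| 4 or more, and FAH | 4/4 = 100% | 4/14 = 28.6% |

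The row for end of treatment depends on each child's treatment duration, which section 9.2.4.2 leaves to the physician.

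Shift in the pooled mean VAS change with no change in health = share of pairs that switch × mean proxy-self difference. The difference is assumed at 3, 5 or 10 points; its sign is not known.

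- Year one: 0.071 × 3 = 0.2; 0.071 × 5 = 0.4; 0.071 × 10 = 0.7 points.
- FAH: 0.286 × 3 = 0.9; 0.286 × 5 = 1.4; 0.286 × 10 = 2.9 points.

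Within the switched children themselves the shift is the whole assumed difference, 3 to 10 points; the pooled mean dilutes it. Within proxy-proxy and self-self pairs the rater-switch part is zero. The same mixing affects the five dimensions, but the documents give nothing from which to size it.

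**The case against.** The strongest objection is that this belongs in the statistical analysis plan. Section 9.7.2.1 sends the detailed analysis and table templates there, and section 9.7.2.6 refers back to section 9.3.2.5, where the two versions are defined. Nothing says outright that proxy and self ratings will be pooled, and the unseen plan may split them. That is fair as to table layout. It does not remove the point, because the protocol itself fixes both the age-based switch and a change from baseline for everyone aged 4 and over. Followed as written, that subtracts a parent's rating from a child's.

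A second objection concerns consequence, and it stands. Section 9.7.2.1 makes the analyses primarily descriptive, with no formal testing. A reader might infer that the rater switch will pass as a treatment effect on quality of life. The documents do not support that: the registry is uncontrolled, and change over years of growth and puberty could not be attributed to treatment whoever does the rating.

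A third concerns size. A reader might assume that most pairs switch; 70% switching with a 10-point difference would give 0.7 × 10 = 7 points. The documents give no start-age distribution, and 70% would need a cohort that starts much younger than the even spread used here. Nor do they give a proxy-self difference or its direction, so a mean difference near zero cannot be excluded.

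**Conclusion.** The point holds as one of definition: the stated change from baseline combines two measures for children who start at 4 to 7 and later self-complete. The size is unknown. Under the even-start assumption and an assumed 3 to 10 point difference in either direction, the pooled mean VAS change would move by about 0.2 to 0.7 points at year one and 0.9 to 2.9 points at FAH.

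Three stronger readings should be avoided.

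- Not every child who starts at 4 to 7 has switched by end of treatment. Treatment may stop before age 8, and some children stay on the proxy form.
- Year one is affected only through children who start at 7.
- The version cannot be taken as already available for analysis at each visit. The documentation sentence is worded per participant and refers to the medical records, so capture per assessment in the eCRF is not assured.

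This is a worthwhile correction to a descriptive secondary endpoint. It does not touch the primary safety analysis.

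**What to change.** In section 9.3.2.5, require the version (proxy or self) to be recorded in the eCRF at each assessment, not once per participant.

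In section 9.7.2.6, describe the dimensions and the VAS by version at each timepoint. Report change from baseline separately for proxy-proxy, self-self and proxy-self pairs. Give no single mean pooled across version pairs, and interpret change in health from the same-version pairs.

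The proxy-self pairs should be shown, not dropped. Dropping them would take nearly all children who started at 4 to 7 out of the FAH results and replace a rater problem with selection by start age.

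The cost is a change of wording and possibly one added eCRF field. The strata become smaller, chiefly at end of treatment and FAH, where the same-version pairs will come mainly from children who started at 8 or over. The report should say so.
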